Appendix 6: Blood specimen Flow chart in pre-selected centers

Appendix 7: Declaration of Helsinki

Declaration of Helsinki

World Medical Association Declaration of Helsinki: Ethical Principles for Medical Research Involving Human Subjects

Adopted by the 18th WMA General Assembly Helsinki, Finland, June 1964 and amended by the 29th WMA General Assembly, Tokyo, Japan, October 1975 35th WMA General Assembly, Venice, Italy, October 1983 41st WMA General Assembly, Hong Kong, September 1989 48th WMA General Assembly, Somerset West, Republic of South Africa, October 1996 and the 52nd WMA General Assembly, Edinburgh, Scotland, October 2000

A. INTRODUCTION

1. The World Medical Association has developed the Declaration of Helsinki as a statement of ethical principles to provide guidance to physicians and other participants in medical research involving human subjects. Medical research involving human subjects includes research on identifiable human material or identifiable data.
2. It is the duty of the physician to promote and safeguard the health of the people. The physician's knowledge and conscience are dedicated to the fulfillment of this duty.
3. The Declaration of Geneva of the World Medical Association binds the physician with the words, "The health of my patient will be my first consideration," and the International Code of Medical Ethics declares that, "A physician shall act only in the patient's interest when providing medical care which might have the effect of weakening the physical and mental condition of the patient."
4. Medical progress is based on research which ultimately must rest in part on experimentation involving human subjects.
5. In medical research on human subjects, considerations related to the well-being of the human subject should take precedence over the interests of science and society.
6. The primary purpose of medical research involving human subjects is to improve prophylactic, diagnostic and therapeutic procedures and the understanding of the aetiology and pathogenesis of disease. Even the best proven prophylactic, diagnostic, and therapeutic methods must continuously be challenged through research for their effectiveness, efficiency, accessibility and quality.
7. In current medical practice and in medical research, most prophylactic, diagnostic and therapeutic procedures involve risks and burdens.
8. Medical research is subject to ethical standards that promote respect for all human beings and protect their health and rights. Some research populations are vulnerable and need special protection. The particular needs of the economically and medically disadvantaged must be recognized. Special attention is also required for those who cannot give or refuse consent for themselves, for those who may be subject to giving consent under duress, for those who will not benefit personally from the research and for those for whom the research is combined with care.
9. Research Investigators should be aware of the ethical, legal and regulatory requirements for research on human subjects in their own countries as well as applicable international requirements. No national ethical, legal or regulatory requirement should be

allowed to reduce or eliminate any of the protections for human subjects set forth in this Declaration.

B. BASIC PRINCIPLES FOR ALL MEDICAL RESEARCH

1. It is the duty of the physician in medical research to protect the life, health, privacy, and dignity of the human subject.
2. Medical research involving human subjects must conform to generally accepted scientific principles, be based on a thorough knowledge of the scientific literature, other relevant sources of information, and on adequate laboratory and, where appropriate, animal experimentation.
3. Appropriate caution must be exercised in the conduct of research which may affect the environment, and the welfare of animals used for research must be respected.
4. The design and performance of each experimental procedure involving human subjects should be clearly formulated in an experimental protocol. This protocol should be submitted for consideration, comment, guidance, and where appropriate, approval to a specially appointed ethical review committee, which must be independent of the investigator, the sponsor or any other kind of undue influence. This independent committee should be in conformity with the laws and regulations of the country in which the research experiment is performed. The committee has the right to monitor ongoing trials. The researcher has the obligation to provide monitoring information to the committee, especially any serious adverse events. The researcher should also submit to the committee, for review, information regarding funding, sponsors, institutional affiliations, other potential conflicts of interest and incentives for subjects.
5. The research protocol should always contain a statement of the ethical considerations involved and should indicate that there is compliance with the principles enunciated in this Declaration.
6. Medical research involving human subjects should be conducted only by scientifically qualified persons and under the supervision of a clinically competent medical person. The responsibility for the human subject must always rest with a medically qualified person and never rest on the subject of the research, even though the subject has given consent.
7. Every medical research project involving human subjects should be preceded by careful assessment of predictable risks and burdens in comparison with foreseeable benefits to the subject or to others. This does not preclude the participation of healthy volunteers in medical research. The design of all studies should be publicly available.
8. Physicians should abstain from engaging in research projects involving human subjects unless they are confident that the risks involved have been adequately assessed and can be satisfactorily managed. Physicians should cease any investigation if the risks are found to outweigh the potential benefits or if there is conclusive proof of positive and beneficial results.
9. Medical research involving human subjects should only be conducted if the importance of the objective outweighs the inherent risks and burdens to the subject. This is especially important when the human subjects are healthy volunteers.
10. Medical research is only justified if there is a reasonable likelihood that the populations in which the research is carried out stand to benefit from the results of the research.
11. The subjects must be volunteers and informed participants in the research project.

12. The right of research subjects to safeguard their integrity must always be respected. Every precaution should be taken to respect the privacy of the subject, the confidentiality of the patient's information and to minimize the impact of the study on the subject's physical and mental integrity and on the personality of the subject.

13. In any research on human beings, each potential subject must be adequately informed of the aims, methods, sources of funding, any possible conflicts of interest, institutional affiliations of the researcher, the anticipated benefits and potential risks of the study and the discomfort it may entail. The subject should be informed of the right to abstain from participation in the study or to withdraw consent to participate at any time without reprisal. After ensuring that the subject has understood the information, the physician should then obtain the subject's freely-given informed consent, preferably in writing. If the consent cannot be obtained in writing, the non-written consent must be formally documented and witnessed.

14. When obtaining informed consent for the research project the physician should be particularly cautious if the subject is in a dependent relationship with the physician or may consent under duress. In that case the informed consent should be obtained by a well-informed physician who is not engaged in the investigation and who is completely independent of this relationship.

15. For a research subject who is legally incompetent, physically or mentally incapable of giving consent or is a legally incompetent minor, the investigator must obtain informed consent from the legally authorized representative in accordance with applicable law. These groups should not be included in research unless the research is necessary to promote the health of the population represented and this research cannot instead be performed on legally competent persons.

16. When a subject deemed legally incompetent, such as a minor child, is able to give assent to decisions about participation in research, the investigator must obtain that assent in addition to the consent of the legally authorized representative.

17. Research on individuals from whom it is not possible to obtain consent, including proxy or advance consent, should be done only if the physical/mental condition that prevents obtaining informed consent is a necessary characteristic of the research population. The specific reasons for involving research subjects with a condition that renders them unable to give informed consent should be stated in the experimental protocol for consideration and approval of the review committee. The protocol should state that consent to remain in the research should be obtained as soon as possible from the individual or a legally authorized surrogate.

18. Both authors and publishers have ethical obligations. In publication of the results of research, the investigators are obliged to preserve the accuracy of the results. Negative as well as positive results should be published or otherwise publicly available. Sources of funding, institutional affiliations and any possible conflicts of interest should be declared in the publication. Reports of experimentation not in accordance with the principles laid down in this Declaration should not be accepted for publication.

C. ADDITIONAL PRINCIPLES FOR MEDICAL RESEARCH COMBINED WITH MEDICAL CARE

1. The physician may combine medical research with medical care, only to the extent that the research is justified by its potential prophylactic, diagnostic or therapeutic value. When medical research is combined with medical care, additional standards apply to protect the patients who are research subjects.

2. The benefits, risks, burdens and effectiveness of a new method should be tested against those of the best current prophylactic, diagnostic, and therapeutic methods. This

does not exclude the use of placebo, or no treatment, in studies where no proven prophylactic, diagnostic or therapeutic method exists.

3. At the conclusion of the study, every patient entered into the study should be assured of access to the best proven prophylactic, diagnostic and therapeutic methods identified by the study.

4. The physician should fully inform the patient which aspects of the care are related to the research. The refusal of a patient to participate in a study must never interfere with the patient-physician relationship.

5. In the treatment of a patient, where proven prophylactic, diagnostic and therapeutic methods do not exist or have been ineffective, the physician, with informed consent from the patient, must be free to use unproven or new prophylactic, diagnostic and therapeutic measures, if in the physician's judgment it offers hope of saving life, re-establishing health or alleviating suffering. Where possible, these measures should be made the object of research, designed to evaluate their safety and efficacy. In all cases, new information should be recorded and, where appropriate, published. The other relevant guidelines of this Declaration should be followed.

References

SAP	Statistical Analysis Plan
ICH	International Conference on Harmonization of Technical Requirements for Registration of Pharmaceuticals for Human Use
ER	Estrogen receptor
PGR	Progesterone receptor
EOS	End of study
EOT	End of treatment
FPI	First patient in
HER	Human epithelial growth factor receptor
IHC test	Immunohistochemistry test
FISH test	Fluorescence In Situ Hybridization test
LPLV	Last patient last visit
ITT	Intention to treat
TTPd	Time to distant progression
TTPl	Time to local progression
CEA	Carcinoembryonic antigen
CA 15-3	Carcinoma antigen 15-3
QoL	Quality of Life

1. Introduction

This Statistical Analysis Plan (SAP) is based on the Clinical Study Protocol for the ABCSG study 28 in version 4.0 from Sep 06, 2011 and provides a detailed description of all statistical analyses planned to be conducted within this trial at predefined time points.

All analyses described herein are performed in accordance to the guidelines of the International Conference on Harmonisation of Technical Requirements for Registration of Pharmaceuticals for Human Use (ICH).

2. Study details

This study is a prospective, randomized, multicentre, study concerning the influence of local treatment on the patients with synchronous metastasized breast cancer. Patients are stratified at inclusion according to the centre, the hormone-receptor status (ER-/PR-/not determinable; any PR and/or Er+), the HER-2 status (positive vs. negative/not determinable), the grading (G1/G2 vs. G3/not determinable), location of metastases (visceral ± vs bone only), and use of first line chemotherapy (anthracyclin-based ± any other, except taxan, vs. taxan-based ± any other vs. other therapies, e.g. antihormonal therapy alone).

The aim of the study is to evaluate the median survival (primary objective) of patients with synchronous metastasized breast cancer and the primary tumor in place comparing arm A with local therapy (lumpectomy or mastectomy + axillary surgery /± radiotherapy) to the primary tumor versus arm B without local therapy (surgery on demand). Systemic therapy is administered at the centers policy.

2.1. Study design

2.1.1. Study duration

4 years recruitment period and maximum study duration of 9 years

2.1.2. End of study

1. Withdrawal of informed consent
2. Death
3. Lost to Follow Up

2.2. Study objectives

2.2.1. Primary objective

The primary objective is to demonstrate that the resection of the primary breast cancer in synchronous metastasized breast cancer patients increases the median survival.

2.2.2. Secondary objectives

The secondary study objectives are

1. to investigate the role of the primary breast cancer resection in terms of local and distant time to progression
2. to evaluate the role of peripheral circulating tumor cells and growth factors in synchronous metastasized breast cancer patients and whether there is any association between their detection and the median survival in pre-selected centers
3. to examine whether the resection of the primary breast cancer influences peripheral circulating tumor cells and growth factors in pre-selected centers
4. to investigate the quality of life (QoL) in both groups

2.2.3. Safety objectives

The safety objective for this study is to evaluate the safety of surgical therapy and local therapy versus no surgery (surgery on demand) and local therapy.

2.3. Randomization and stratification criteria

The randomization system used is the software ‘Randomizer’ which was developed and is maintained by the Institute of Medical Statistics and Informatics at the Medical University of Vienna. In accordance to the inclusion and exclusion criteria, patients are randomized to one of the following arms:

A: Surgical Therapy
 B: Surgery on Demand

Patients were stratified with respect to following stratification factors:

- Center
- Grading
 - G1/G2 **versus** G3/GX
- Receptor status
 - 0/0 **versus** any positive
- Her2neu status
 - FISH amplified/IHC+++ **versus** negative
- Location of metastases
 - visceral ± **versus** bone only
- Planned first line therapy
 - Anthracycline-based ± any other except taxane **versus** taxane based ± any other **versus** any other therapy

2.4. Number of subjects - sample size estimation

A sample of 254 patients will be enrolled in this trial (127 in each group) including a drop out rate of 5%. This assumes that there will be a 48-month accrual period. The maximum study duration should be 9 years.

The sample size is estimated for the primary endpoint. The median survival of patients with local therapy to the primary tumor should be increased by 50% in comparison to patients without local therapy to have 80% power to detect a hazard ratio of 0.666 with a two-sided significance level of 0.05. The recruitment period is assumed with 4 years

3. Statistical methods

3.1. Data handling conventions

3.1.1. Data entry errors and potential outliers

Patients may have potential outliers for particular observations. Observations will be checked for correctness by the study team before data freeze and at the time point of data freeze all data should be correct. Values found to be incorrect due to data entry error after data freeze will be excluded from all analyses as missing values. Incidence of incorrect values and potential outliers will be listed and summarized by treatment arm.

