2. In premenopausal patients anti-hormonal treatment - if indicated - should always be coupled with ovarian ablation (surgical resection or systemic endocrine treatment, e.g. with goserelin) to ensure complete hormonal blockade.

3. In postmenopausal patients the primary anti-hormonal treatment - if indicated - should be an aromatase inhibitor (if there are no contraindications).
4. Chemotherapy – if indicated - should precede anti-hormonal treatment – if indicated.

Follow up (Appendix 4)

Routine laboratory tests for safety assessment of palliative systemic therapy and radiological follow up are performed according to the centers' guidelines with the recommended procedures as follows:

- Clinical examination and laboratory tests (red and white blood cells, Tumor marker CA15-3 and CEA) before and every 2-4 months after randomization. After two years examinations should be done every 5-7 months.
- CT scan of the liver and the lung before and every 2-4 months after randomization. Alternatively a PET-CT scan can be performed. Ultrasound of the liver or chest X-ray is only recommended in cases of contraindication for CT. After two years examinations should be done every 5-7 months.
- CT scan or alternatively PET-CT scan of bone metastases (if diagnosed) before and in case of pre-randomization diagnosed bone metastases every 2-4 months after randomization or in case of suspect new bone metastases anytime after randomisation for diagnostic imaging. After two years examinations should be done every 5-7 months.
- EORTC QLQ-C30 and QLQ-BR23 quality of life (Appendix 5) sheets before and every 6 months after treatment until 24 months visit, then every 12 months until 48 months visit.

Blood specimens in pre-selected centers (Appendix 6)

15ml of blood are drawn before surgery and 1-3 days after surgery (arm A only), as well as before first application of systemic therapy, 3-6 months and 12 months after first application of systemic therapy in arm A and arm B.

Tissue specimens in pre-selected centers

Tumor tissue from core needle biopsies before systemic therapy (arm B no local therapy group) or from surgical resections (arm A local therapy group) are used for further immunhistochemical and flow cytometry analyses. Only in pre-selected centers with experimental background.

Measurements of VEGF and TGF beta in pre-selected centers

Blood

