3.1.2. Missing data

Subjects may have missing specific data points for a variety of causes. In general, data may be missing due to a missed visit, non-evaluability of a specific clinical measurement at its planned clinical visit or a subject's early withdrawal from study. The general procedures outlined below describe what will be done when a data point is missing.

3.1.2.1. *Imputations of missing data*

Generally, only evaluable measurements are considered for the analyses. No values are imputed for missed or non-evaluable visits. In case of primary and secondary efficacy endpoints possible specific requirements are stated in the according analysis sections.

3.1.2.2. *Partial Dates*

Partially incomplete dates (day or day/month missing) will be imputed for dates of progression as well as for therapy begin and/or end dates. Completely missing dates and missing years will not be imputed.

Imputation Rules for Partial Progression Dates

	Missing	Impute	Exception
Event Date	Day	01	Default to Day 1 of the study if an event started the same year and month as Day 1
	Day /Month	01JAN	Default to Day 1 of the study if an event started the same year as Day 1

Imputation Rules for Partial Therapy Start and Stop Dates

	Missing	Impute	Exception
Start date	Day	01	Default to Day 1 of the study if a therapy started the same year and month as Day 1
	Day /Month	01JAN	Default to Day 1 of the study if a therapy started the same year as Day 1
Stop date	Day	Last day of the month	Default to the EOS date if the imputed therapy stop date is after the EOS date
	Day/Month	31Dec	

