3.3. Definition of populations for analyses

3.3.1. Intention-to-Treat (ITT) population

Primary and secondary analyses will be based on the Intention-to-Treat (ITT) population; that is, all patients who were included in the randomization. All subjects will be analyzed according to the therapy arm to which they have been randomized. Subjects who terminate the study before their scheduled final study visits will be censored.

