3.5. Primary endpoint evaluation

3.5.1. Primary endpoint

Median survival time will be compared through overall survival. Overall survival (OS) is determined by the time from randomization to death including breast cancer-related deaths and deaths from any other cause. If the patient is alive at the end of the observation period, the patient will be censored.

The null and alternative hypotheses for the primary endpoint are as follows:

- H0: Overall survival is equal in patients receiving local therapy (surgery) compared to patients receiving no local therapy (surgery on demand)
- H1: Overall survival differs between patients receiving local therapy (surgery) compared to patients receiving no local therapy (surgery on demand)
-

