3.5.2. Data set for primary endpoint

Data analysis for the primary endpoint will be based on the ITT-population. Subjects who terminate the study before their scheduled final study visits will be censored at the time of their last contact.

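### SAP 3.1.2.2 sets no floor at the last progression-free assessment when it imputes year-only progression dates; secondarily, SAP 3.1.1 voids post-freeze errors that source could correct

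*SAP*

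**What the plan says.** **Partial progression dates.** SAP 3.1.2.2 fills in progression dates that lack the day, or the day and month. When both are missing, the date becomes 1 January of the recorded year, with one exception: "Default to Day 1 of the study if an event started the same year as Day 1". Day 1 is therefore the only lower bound. Dates without a year are left alone: "Completely missing dates and missing years will not be imputed". The imputation covers progression and therapy dates; death dates are not named. SAP 3.1.2.1 allows for special requirements in the endpoint sections, but SAP 3.5 and 3.6 contain none on this point. SAP 3.6.1 runs TTPd and TTPl from randomization.

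**Assessments on file.** The protocol's Follow up section recommends frequent imaging: "CT scan of the liver and the lung before and every 2-4 months after randomization", moving to every 5-7 months after two years. The Appendix 4 flowchart shows CT at months 3, 6, ..., 24, then every six months to 60. Breast imaging is firmly marked once a year and only in brackets at the other visits.

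**Errors found after freeze.** SAP 3.1.1 says: "Values found to be incorrect due to data entry error after data freeze will be excluded from all analyses as missing values". It adds only a report: "Incidence of incorrect values and potential outliers will be listed and summarized by treatment arm". For overall survival, SAP 3.5.1 counts death from any cause and says: "If the patient is alive at the end of the observation period, the patient will be censored". SAP 3.5.2 says: "Subjects who terminate the study before their scheduled final study visits will be censored at the time of their last contact".

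**The concern.** The date rule does not use what the trial already knows. A patient with dated, clean scans through August and progression recorded only by year is treated as having progressed on 1 January. The analysis file would then hold an event time that the patient's own scans contradict. The error always runs early, so Kaplan-Meier curves and medians for TTPd and TTPl are pulled down in proportion to the share of such dates. If year-only dates were commoner in one arm, the comparison would shift as well.

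The post-freeze rule raises a separate, smaller issue. It applies to every analysis, including the primary one, and makes no exception for values that source records can correct. If the voided value is a death date, no rule restores it, and the SAP does not say how that known death is to be analysed.

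**Working it through.** **1. One hypothetical patient.** Randomized 15 Feb 2011, last clean visit 15 Aug 2012, progression found 15 Nov 2012 but recorded only as 2012 (30.4375 days per month).

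- Actual time: 639 days = 21.0 months.
- SAP rule (1 Jan 2012): 320 days = 10.5 months.
- Floor at the last clean visit: 547 days = 18.0 months.

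The SAP date falls 18.0 - 10.5 = 7.5 months before a visit that found no progression.

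**2. Average shift per year-only date.** The documents give no figure to reproduce here. Assumptions: exponential time to progression, median 6 to 36 months; events within 60 months; randomization uniform over the calendar year; CT visits as in Appendix 4, all attended. With r the month of the year at randomization and t the event time:

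- SAP time = max(0, 12 x floor((r + t)/12) - r)
- Time with floor = max(SAP time, last clean visit)
- Shift = t minus the imputed time

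Model A uses exact event times; model B dates the event at the detecting visit. There were 600,000 simulated patients per row. Shifts are in months.

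| Median | A: SAP shift | A: with floor | A: before a clean scan | A: set to Day 1 | B: SAP shift | B: with floor | B: before a clean scan | B: set to Day 1 |
|---|---|---|---|---|---|---|---|---|
| 6 | 3.97 | 1.35 | 62% | 46% | 4.64 | 2.74 | 51% | 36% |
| 12 | 4.79 | 1.57 | 71% | 29% | 5.19 | 3.05 | 57% | 22% |
| 18 | 5.09 | 1.70 | 73% | 22% | 5.39 | 3.24 | 58% | 17% |
| 24 | 5.22 | 1.78 | 74% | 19% | 5.49 | 3.36 | 58% | 14% |
| 36 | 5.37 | 1.87 | 75% | 16% | 5.59 | 3.49 | 57% | 12% |

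Hand check of the Day 1 share, model A, median 12: [1 - (1 - e^(-12λ))/(12λ)] / (1 - e^(-60λ)) with λ = ln 2/12 gives (1 - 0.5/0.693)/0.969 = 0.288, or 29%.

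The largest shift is 12 months under the SAP rule and 6 with the floor. Dates missing only the day are about 0.5 months early and are not at issue.

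**3. TTPl.** If only the firm annual breast imaging counts as an assessment, 15-36% of year-only dates precede a clean one in model A and 0% in model B. The zero follows because 1 January is never as much as 12 months before a detecting scan in the same year. The problem is mainly one for TTPd.

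**4. Trial level.** The mean shift is the share of year-only dates times the shift per date. In model B with median 12, shares of 1%, 5% and 10% give 0.05, 0.26 and 0.52 months, against 0.03, 0.15 and 0.31 with the floor. Model A, with true medians of 12 and 18 months, 300,000 per arm and equal shares in both arms:

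| Year-only share | Medians, SAP rule | Medians, floor | HR, SAP rule (true 0.667) |
|---|---|---|---|
| 5% | 11.8 and 17.7 | 12.0 and 17.9 | 0.671 |
| 10% | 11.5 and 17.4 | 12.0 and 17.9 | 0.671 |
| 20% | 11.0 and 17.0 | 12.0 and 18.0 | 0.667 |

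Simulation error of the HR is about 0.002. In model B the HR is 0.686-0.690, against 0.689 with complete scan dates. Its medians move only in whole visit steps, and at 12 and 18 months they did not move even with a 20% share.

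**5. Secondary point: what a lost death would cost.** The plan's event count first: 4(1.96 + 0.8416)²/(ln 0.666)² = 190.03, so 191 against the stated 192. Fixed-design power is Φ(√D/2 x ln 1.5 - 1.96):

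- D = 192: 80.2%
- D = 191: 80.0%
- D = 187: 79.2%
- D = 182: 78.1%

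Each death lost from the analysis would cost about 0.2 points. The losses of 5 and 10 are illustrations only.

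**The case against.** **On the date rule.** The modelled record is an unlikely one: every earlier scan attended, dated and clean, yet the progression known only by year. If the clean scans are dated, the detecting scan usually is too. Year-only dates seem likelier where visits were missed or care took place elsewhere, and then fewer clean scans exist to contradict them. The schedule is also only recommended. This stands. A reader might take the 51-75% falling before a clean scan as a rate for the trial; it is conditional on that pattern and cannot be read so. What remains is that the rule, followed as written, permits the contradiction, and nothing in SAP 3.5 or 3.6 prevents it.

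**On Day 1.** A reader might also object that Day 1 is undefined. That is trivial, since SAP 3.5.1 and 3.6.1 run time from randomization.

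**On the post-freeze rule.** A reader might infer that the SAP directs a known death to be censored. It does not. SAP 3.1.1 voids the incorrect value, not the fact of death. Death is recorded separately as an end-of-study reason (SAP 2.1.2) and by cause (SAP 3.4.1), and SAP 3.5.1 provides for censoring a patient who is alive. Applying the early-termination rule of SAP 3.3.1 and 3.5.2 to a patient known to be dead would sit badly with that. The SAP is silent on the case. The case should also be rare: the protocol has monitors verify the CRFs at regular intervals, SAP 3.1.1 checks values before freeze, and SAP 3.2.1 places data cleaning before the primary analysis. Barring later edits also guards against selective correction in a trial where surgery reveals the arm. Exclusion against re-freeze is therefore partly a trade-off, which is why this point is secondary.

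**Conclusion.** The point holds as a minor one. The missing floor is a flaw in a stated rule, and it can produce TTPd and, less often, TTPl event times that documented assessments contradict. Per year-only date the rule is about 4.0-5.6 months early; a floor leaves about 1.4-3.5 months. Both ranges assume median times to progression of 6-36 months and attended visits.

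The number of such dates is not given. At a share of 1-2% the medians would move by about 0.1 month or less. The hazard ratio hardly changes if incompleteness is similar in the two arms; imbalance could change that, but the documents give no sign of it. Overall survival is not affected by this rule.

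On post-freeze errors, the supportable conclusion is narrower: a value that source could correct is discarded, and the handling of a known death with a voided date is unspecified. No stated figure in the plan is wrong on either count.

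**What to change.** **SAP 3.1.2.2.** Where the detecting assessment is dated, use that date. Otherwise set a partial progression date to the latest of 1 January of the recorded year, the randomization date, and the last assessment free of that type of progression (distant for TTPd, local for TTPl). The result must be no later than the first assessment documenting progression, death or last contact. Use actual assessment dates, since the visit schedule is only recommended.

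**SAP 3.1.1.** Keep the frozen-data analysis. Add a sensitivity analysis in which errors verified against source are corrected under a documented procedure with an audit trail, decided without knowledge of arm or results. In it, a patient known to have died is an event at the source-verified date. State in advance what is done if source gives no usable date.

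**Cost.** Two SAP paragraphs, minor programming and possibly a documented unfreeze. Design, sample size and patient care do not change. Both rules should be settled before the data are frozen.
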